#### **4.8.1 INDICATIONS AND USAGE:**

Revlimid® (lenalidomide) is indicated for the treatment of patients with transfusion-dependent anemia due to Low- or Intermediate-1-risk myelodysplastic syndromes associated with a deletion 5q cytogenetic abnormality with or without additional cytogenetic abnormalities. Revlimid® is also approved in combination with dexamethasone for the treatment of patients with multiple myeloma that have received at least one prior therapy.

#### **4.9 Adverse Events**

Most frequently reported adverse events reported during clinical studies with lenalidomide in oncologic and non-oncologic indications, regardless of presumed relationship to study medication include: anemia, neutropenia, thrombocytopenia and pancytopenia, abdominal pain, nausea, vomiting and diarrhea, dehydration, rash, itching, infections, sepsis, pneumonia, UTI, Upper respiratory infection, cellulites, atrial fibrillation, congestive heart failure, myocardial infarction, chest pain, weakness, hypotension, hypercalcemia, hyperglycemia, back pain, bone pain, generalized pain, dizziness, mental status changes, syncope, renal failure, dyspnea, pleural effusion, pulmonary embolism, deep vein thrombosis, CVA, convulsions, dizziness, spinal cord compression, syncope, disease progression, death not specified and fractures.

Tumor flare reaction (TFR) has been reported frequently in CLL patients treated with lenalidomide. Tumor lysis syndrome (TLS) has been reported in CLL patients treated with lenalidomide. Precautions must be taken to prevent TLS including proper selection of patients with regard to renal function, correction of electrolyte abnormalities, and TLS prophylaxis and monitoring. Lenalidomide has been shown to increase the level of digoxin in the blood in some patients.

Complete and updated adverse events are available in the Investigational Drug Brochure and the IND Safety Letters.

#### **4.10 Rational for Treatment in this Setting**

**Selection of patients:** The first Revlimid® study reported by List et al included all transfusion dependent MDS patients, but given the early experience which showed a better response in del(5q) patients and those with lower risk disease, more patients belonging to this category were entered on the trial. The subsequent multi-center studies were focused entirely on the low/Int-1 patients who were transfusion dependent. In the present study, we would like to recapitulate the initial study by only treating the transfusion dependent, low and intermediate-1 risk MDS patients without deletion (5q). Since the predictive assay is most applicable for the non-del(5q) patients, and to avoid confusion resulting from an admixture of patients with del(5q) for whom the drug is already FDA approved, we have elected to restrict this clinical trial to only the non-del(5q) patients.

**Current Protocol:** In the present study, only the non-del(5q) transfusion dependent, low and intermediate-1 risk MDS patients will be treated with single agent Revlimid®. All patients will have their pre-therapy bone marrows studied by gene expression **microarray, Luminex bead assay, and real-time PCR.**

### **5 Study Objectives and Endpoints**

#### **5.1 Objectives**

##### **5.1.1 Primary Objective**

To conduct a prospective trial testing the Revlimid® (lenalidomide) response signature in patients who have transfusion dependent, non-del(5q), low and intermediate-1 risk myelodysplastic syndromes (MDS) in order to confirm the predictive value of the signature and to establish the boundaries of the z-score which can be used to pre-select patients in future clinical studies.

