### **Multi-institutional experience (MDS 002 and 003 trials):**

**Revlimid® in del(5q) patients:** The List experience described above was followed by a multicenter Phase II study (42) evaluating the efficacy of REVIMID® in transfusion dependent (TD)-MDS pts with del5q31. A multicenter Phase II trial (MDS 003) for transfusion dependent low to Int-1 del(5q) patients

showed remarkable results. Among 148 pts with del(5q31), 111 had this as an isolated cytogenetic abnormality, and 37 patients had additional chromosomal changes. The median age was 71 years (range, 37-95) with 66% females and 146 patients had a confirmed transfusion dependence. In an intent-to-treat analysis, transfusion independence was achieved in 99 patients (67%) with a median 5.3/dl hemoglobin increase (range: 1.1-11.4/dl). The median time to response was 4 weeks (range: 3.6-5.3 weeks). The transfusion independence rate was greater in patients with isolated del(5q) abnormality (69% versus 49%;  $p=0.003$ ). Cytogenetic response ( $\geq 50$  decrease in abnormal metaphases) was achieved in 70% of transfusion independent patients with 44% achieving a complete cytogenetic remission. Pathologic complete remission was documented in 32/110 (29%) evaluable patients. After a median follow-up of 9.3 months (range: 4.2 to 14.8+ months), the median response duration is not reached with only 10 responders (9%) failing.

**Revlimid® in non-del(5q) patients:** The results of Revlimid® treatment of transfusion dependant low to Int-1 patients without the del(5q) has also shown that Revlimid® is an effective treatment option (43). A total of 214 patients were treated with Revlimid® (MDS 002). Overall, 56 (26%) of 214 enrolled patients achieved transfusion independence. Median time to response was 5 weeks, median duration of response was 41.0 weeks (range, 8.0-136.4), and median Hgb increase achieved was 3.2 g/dL (range, 1.0-9.8). An additional 36 patients experienced a  $\geq 50\%$  reduction in RBC transfusions (hematological improvement in 92 [43%] patients). Of 47 (22%) patients who had an abnormal karyotype at baseline, 9 (19%) patients achieved a cytogenetic response (4 complete). These early findings indicate that Revlimid® has significant erythroid activity in patients with low- to int-1-risk MDS.

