## **5.2 Endpoints**

### **5.2.1 Primary Endpoint**

- Assessment of pre-therapy gene expression profile associated with Revlimid® responsiveness.

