## 11 Biostatistical Analysis

### 11.1 Overview

The aim of the study is to compare the diagnostic ability of the gold standard microarray assay to the Luminex Bead assay and to quantitative real-time PCR assay in order to detect Revlimid®-response in patients with MDS. Earlier studies have shown microarray assay to identify responders with a sensitivity of 94% and a specificity of 86% (44). It is hypothesized that the less expensive and more clinically useful Luminex Bead assay will predict MDS Revlimid® responders with a sensitivity of 75% and a specificity of 70% compared to criterion gold standard microarray assay. However, it may be possible that real-time PCR will also be equally useful clinically and an easier assay to perform in the clinical lab setting as many pathology laboratories are now equipped with the necessary instrumentation. We will thus compare both the Luminex and real-time PCR assays, assuming the same level of sensitivity and specificity for each, to the gold standard microarray assay. These levels would be 80% of the sensitivity and specificity of the gold standard.

To test this hypothesis, a paired design will be used with each subject being tested with both diagnostic tests [microarray versus either Luminex or PCR; (written "Luminex" in the formula)]. The null hypothesis is that the difference in sensitivity rates will be more than 0.80, and the alternative hypothesis will be that the difference in rates will be less or equal to 0.80. Using the sample size formula:

$$n = \left( \frac{z_{(1-\beta)} + z_{(1-\alpha)}}{\log(\gamma/\delta)} \right)^2 \left( \frac{(\gamma+1)TPR(luminex) - 2(concordance\ probability)}{\gamma(TPR\ luminex)^2} \right)$$

Where  $1-\beta$  is the power (0.80) and  $\alpha$  is the Type I error rate (0.95),  $\delta$  is the percentage difference between the microarray assay true positive rate (TPR) and the luminex TPR. The concordance probability is the estimated percentage of both tests having concordant true positives. Using the estimated concordance of 50%, an estimated 100 subjects will be required. With concordance set at 60%, an estimated 59 subjects will be required. (Alonso, T Sample size calculations for comparative studies of medical tests for detecting presence of disease. Stats in medicine 2002; 21:835-852)

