### 11.2 Analysis of Clinical Response

- Response will be evaluated **every 4 weeks during the first 12 weeks** of therapy for each of the 56 transfusion-dependent low/Int-1 risk MDS patients. Treatment will be stopped and the patient will be taken off the protocol in case of no response or stable disease by 12 weeks. International Working Group (**IWG 2006**) **criteria** will be used for response evaluation. The proportion of TI will be calculated and an exact 95% confidence interval of TI proportion will be estimated. The percent of major and minor responses in erythroid,

platelets, neutrophils, bone marrow and cytogenetic will also be calculated as the secondary endpoints.

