streptavidin-coated phycoerythrin, the labeled amplicons will be annealed to capture probe-linked fluorescent microspheres. Microspheres are detected by flow cytometry and captured labeled amplicons are quantified (Luminex) by subtracting background from the mean fluorescent intensity of each bead.

**Real-time PCR:** Total RNA from bone marrow mononuclear cells preserved in Trizol will be used for the Real-time PCR assay for the expression of 32 genes, which includes the 24 genes of interest and controls. Primers for each gene will be designed (Roche Biosystems) such that only the RNA transcript and no genomic DNA will be measured by the Roche Light Cycler quantitative PCR assay. The Sybergreen kit (Roche) which measures relative amount of gene specific transcript will be used. Results will be analyzed with the Roche Light Cycler analysis package.

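### The same 56 patients are to confirm the signature and set its z-score boundaries, with no planned separation or optimism correction, so accuracy quoted at the fitted boundaries would be too favourable

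*Combined protocol and SAP*

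**What the plan says.** Section 5.1.1, repeated in the synopsis, gives the trial one primary objective with two parts: "to confirm the predictive value of the signature and to establish the boundaries of the z-score". The boundaries are meant for use outside this trial, as limits "which can be used to pre-select patients in future clinical studies".

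The primary endpoint in 5.2.1 is "Assessment of pre-therapy gene expression profile associated with Revlimid® responsiveness". It names no statistic, cut-off or success criterion.

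Section 11 does not fill the gap:
- 11.1 compares the Luminex and PCR assays with microarray and sizes that comparison. It reports the earlier microarray result: "Earlier studies have shown microarray assay to identify responders with a sensitivity of 94% and a specificity of 86" per cent. It does not give the z-score cut-off behind that result.
- 11.2 covers clinical response "for each of the 56 transfusion-dependent low/Int-1 risk MDS patients", with an exact interval for the proportion reaching transfusion independence.
- 11.3 says only that marrow is collected and stored.
- 11.4 describes laboratory methods. It does fix the genes as those of the earlier published signature.

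The z-score appears only in the statements of the objective. No formula, locked cut-off, split sample, cross-validation, bootstrap or later validation cohort is described.

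**The concern.** Setting boundaries means choosing them with these patients' responses in view. If sensitivity and specificity are then quoted for the same patients at those boundaries, chance features of the sample that favoured the chosen cut-off are counted as predictive accuracy. The bias always runs in the favourable direction.

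This bears on the primary objective and on later trials. A boundary carried forward with overstated accuracy would select patients less well than promised. This trial also matters for confirmation because the earlier evidence is thin for its population. Section 4.8 reports a training set of 8 responders and 8 non-responders without del(5q), and a test set of 26 that mixed patients with and without del(5q). The present trial enrols only patients without it.

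**Working it through.** **No plan figure to reproduce.** The sample sizes in 11.1 (100 or 59) concern the paired assay comparison. The plan gives no calculation for signature against response or for the boundaries.

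**Inputs from the documents**
- N = 56 (11.2).
- Transfusion independence in the earlier non-del(5q) trial (4.7): "Overall, 56 (26%) of 214 enrolled patients achieved transfusion independence". 0.26 × 56 = 14.6, so 15 responders and 41 non-responders.
- Upper end, same trial: "hematological improvement in 92 [43%] patients". 0.43 × 56 = 24.1, so 24 and 32.
- Accuracy benchmark: 75% sensitivity and 70% specificity, the level 11.1 hypothesises for Luminex and PCR.

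**Assumptions not in the documents**
- Scores are normal with equal variance in responders and non-responders.
- There is one boundary, chosen to maximise J = sensitivity + specificity − 1 (the Youden index) on the 56.
- Where a test is needed at that boundary, it is Fisher's exact test on the same 56.

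**Step 1. Benchmark as a separation of scores.** Mean difference = z(0.75) + z(0.70) = 0.674 + 0.524 = 1.199 standard deviations. AUC = Φ(1.199/√2) = Φ(0.848) = 0.80.

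**Step 2. Apparent against true accuracy at the fitted cut-off, by simulation**

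| True signature | Responders / non-responders | Apparent sens./spec. | Sens./spec. in new patients | Overstatement of J |
|---|---|---|---|---|
| AUC 0.80 | 15 / 41 | 79% / 76% | 69% / 73% | about 0.13 |
| AUC 0.80 | 24 / 32 | 77% / 77% | 70% / 72% | about 0.11 |
| 94% / 86% | 15 / 41 | 94% / 93% | 88% / 91% | about 0.08 |
| No value (AUC 0.50) | 15 / 41 | 64% / 54% | J = 0 | 0.17 |

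For the first row, apparent J is 0.55 and J in new patients is 0.42; 0.55 − 0.42 = 0.13.

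**Step 3. False confirmation of a useless signature, 15 / 41**
- Fisher p < 0.05 at the fitted cut-off: about 13–14% of trials two-sided, 18–19% one-sided.
- Fisher two-sided p < 0.05 in the favourable direction at a cut-off fixed beforehand: 1.6%.
- Rank (AUC) test on the same 56, with no cut-off: 4.9% two-sided.
- Reaching both 75% and 70%: about 0.1% of trials.

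**Step 4. Does correction work, and does it need more patients?**
- Leave-one-out, with the cut-off re-chosen each time, gives a useless signature 51% sensitivity and 50% specificity (J = 0.01), so the optimism is removed.
- At a true 75%/70% with 15 / 41, power is about 84% for Fisher's test at a pre-fixed cut-off and about 97% for the rank test.
- Precision is limited in any case: exact 95% intervals are 45% to 92% for 11/15 and 54% to 84% for 29/41.

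**The case against.** The strongest reply is that the two tasks do not conflict. A rank or AUC test of a prespecified score against response needs no cut-off, and it keeps its error rate while boundaries are explored in the same patients. This stands. A reader might infer from 5.1.1 that one cohort cannot do both jobs; Step 3 shows that it can. The fault is that the plan specifies neither such a test nor any correction.

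Second, the genes are fixed, which rules out the largest source of optimism, re-selecting genes. This also stands, and the figures above already assume that only the cut-off is fitted.

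Third, the Youden rule and Fisher's test are not the plan's. True: the plan names no rule, so the exact sizes are conditional. The direction of the bias is not, provided the cut-off is chosen for good performance on these patients. The 14% also matters only if bare significance counts as confirmation, which the documents do not say. A useless signature would almost never reach 75%/70%.

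A reader might also infer that the best of three assays will be picked, adding further optimism. The documents do not say this: 11.1 makes microarray the reference for the other two. Nor do they show that PCR must take its cut-off from these patients. Section 11.4 says "The Sybergreen kit (Roche) which measures relative amount of gene specific transcript will be used", whereas 4.8 mentions TaqMan for the earlier work. That change makes carry-over of a cut-off uncertain but does not rule it out.

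Finally, no patient in this trial is selected by z-score, so the consequence falls on later studies. That limits the immediate harm but does not correct the estimate passed on to them.

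**Conclusion.** The point holds in a limited form. The plan has the same 56 patients confirm the signature and set its boundaries, and Section 11 contains nothing that keeps the steps apart or adjusts for their overlap. Accuracy quoted at boundaries fitted here would be optimistic. For a signature of about the plan's 75%/70%, sensitivity plus specificity would be overstated by about 0.13 with 15 responders and about 0.11 with 24. For a signature as good as the earlier 94%/86%, the overstatement is nearer 0.08.

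These sizes rest on normal scores, one boundary, the Youden rule and the earlier trial's response rates. More than one boundary, which the plural wording allows, would give more room for fitting. The documents do not support saying that the reported accuracy will certainly be biased, because they do not say how it will be reported.

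**What to change.** Amend 5.1.1 and 11.1 to state two separate aims.

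1. **Confirmation**, using no cut-off fitted to these patients. Either test the prespecified microarray score against response by AUC or rank test, reporting the AUC with a 95% interval; or, if a cut-off can be retrieved from the earlier study, lock it before responses are linked to scores and report sensitivity and specificity at it with exact 95% intervals. The documents do not state that cut-off, so the first option should be written in as the default. The score formula needs to be written down in either case.
2. **Boundary setting**, labelled exploratory. State the rule for choosing the boundaries. Report accuracy at them only as bootstrap optimism-corrected or cross-validated figures, with the choice of cut-off repeated inside each resample. State that the boundaries need validation in a new cohort before they are used to select patients.

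The cost is text and a resampling analysis. Quoted accuracy will be a few points less favourable. No extra patients are needed for the confirmatory test at the assumed 75%/70%, although the intervals for sensitivity will stay wide with about 15 responders. A locked cut-off is credible only if the change is made before responses are linked to scores.

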### **5.1.2 Secondary Objectives**

- The primary clinical efficacy parameter for these patients will be transfusion independence.
- The secondary efficacy parameters for the study will be the remaining criteria as defined by the IWG. The following parameters also will be assessed:
  - Time to disease progression
  - Overall and progression-free survival

## **5.2 Endpoints**

### **5.2.1 Primary Endpoint**

- Assessment of pre-therapy gene expression profile associated with Revlimid® responsiveness.

### **5.2.2 Secondary Endpoints**

- Response will be evaluated **every 4 weeks during the first 12 weeks** of therapy for each of the 56 transfusion-dependent, non-del(5q) low/Int-1 risk MDS patients. Treatment will be stopped and the patient will be taken off the protocol in case of no response or stable disease by 12 weeks. International Working Group (**IWG 2006**) criteria will be used for response evaluation. The proportion of TI will be calculated and an exact 95% confidence interval of TI proportion will be estimated.
- The percent of major and minor responses in erythroid, platelets, neutrophils will also be calculated as the secondary endpoints.

## **6 Investigational Plan**

### **6.1 Overall design**

#### **6.1.1 PRE, INTRA, and POST-THERAPY STUDIES:**

- Bone marrow (BM) aspirate and biopsy
  - All patients must have a BM aspirate and biopsy examination performed within 6 weeks before starting therapy. Routine diagnostic studies include morphology, histochemistry, flow cytometry, immuno-phenotyping, karyotyping, fluorescence in situ hybridization (FISH), cytogenetics. A marrow sample will be saved for the gene

- expression microarray, Luminex bead assay, and real-time PCR.
- A repeat bone marrow aspirate and biopsy will be done at discontinuation from study drug to document complete response, if needed.
  - **Medical/Medication History:** Obtained at screening. Medical history to include diagnoses and any signs/symptoms within prior 28 days. Medication history within prior 28 days and all prior treatment for MDS.
  - **Physical Exam:** Screening, monthly at Day 1 of Cycles 2, 3, and 4 and at Day 1 of every other cycle thereafter, and at discontinuation from study drug, and 30 days (+/- 7 days) following the last dose of study drug.
  - **ECOG Status:** At screening, Day 1 of Cycles 2, 3, and 4, and every other cycle thereafter.
  - **Transfusion History:** Screening, monthly at Day 1 of Cycles 1, 2, 3, each Day 1 study visit thereafter, at discontinuation from study drug, and 30 days (+/- 7 days) following the last dose of study drug.
  - **Hematology** (hemoglobin, hematocrit, RBC indices: RBC count, mean cell volume, mean cell hemoglobin, mean cell hemoglobin concentration; WBC count with differential; and platelet count) at screening, weekly during cycles 1 to 3, and then monthly (i.e., at Day 1 of each cycle) thereafter, at discontinuation from study drug, and 30 days (+/- 7 days) following the last dose of study drug.
  - **Clinical Chemistry** (creatinine, BUN, total bilirubin, alkaline phosphatase, ALT, AST, LDH, total protein) at screening, on Cycle 1 Day 1 and Cycle 1 Day 15 and on Day 1 of Cycles 2, 3, 4 and then as clinically indicated after cycle 4, at discontinuation from study drug, and 30 days (+/- 7 days) following the last dose of study drug. Thyroid stimulating hormone (TSH) will be done at screening Cycle 4 and then every 16 weeks (i.e., Cycles 8, 11, 16, etc.), and at discontinuation from study drug. T3 and T4 levels may be assessed as clinically indicated.
  - All study participants must be registered into the mandatory RevAssist® program, and be willing and able to comply with the requirements of RevAssist®.

- Pregnancy test for women: Females of childbearing potential (FCBP)† must have a negative serum or urine pregnancy test with a sensitivity of at least 50 mIU/mL within 10 – 14 days prior to and again within 24 hours of prescribing lenalidomide. FCBP with regular or no menstruation must have a pregnancy test weekly for the first 28 days and then every 28 days while on therapy (including breaks in therapy), at discontinuation of lenalidomide and at Day 28 post the last dose of lenalidomide. Females with irregular menstruation must have a pregnancy test weekly for the first 28 days and then every 14 days while on therapy (including breaks in therapy), at discontinuation of lenalidomide and at Day 14 and Day 28 post the last dose of lenalidomide (see Appendix I: Risks of Fetal Exposure, Pregnancy Testing Guidelines and Acceptable Birth Control Methods).
- 12-Lead EKG will be performed prior to therapy.
- **MDS-Specific Tests:** at baseline and as clinically appropriate thereafter (serum B12 and erythropoietin). Optional depending on clinical situation: serum iron, total iron-binding capacity (TIBC), ferritin; flow cytometry for CD34.
- **Adverse Events, Toxicity, Concomitant Medications/Procedures:** at each study visits per Schedule of Study Assessments (Section 2), assessed by NCI Common Terminology Criteria for Adverse Events, Ver.3 Note: After Cycle 4, these assessments will be obtained every 8 weeks.
- Patient blood counts, chemistries, transfusion requirements will be reviewed at 4-week intervals with decision for continued therapy at week 12. At the discretion of the Principal Investigator, therapy will be discontinued in the event of a serious adverse event.
- Transfusion criteria: Packed red blood cells (PRBC) will be transfused in case hemoglobin falls below 8.0 Gm/dL or at a higher level in a symptomatic patient. Platelet transfusions will be given only if the patient is showing evidence of bleeding or if at risk of bleeding.

